### 2. Analysis of the secondary endpoints:

To study rosuvastatin effect from baseline to week 48 on mean and / or of left and right maximal IMT progression, multi-levels, repeated measures, linear mixed-effects models adjusted for demographics and/or traditional CVD risk factors and centre will be used. Levels used for the data will be patient and carotid artery locations (CCA, ICA, BIF and ECA) within patients; the repeated measure will be time (baseline and week 48).

Repeated measures linear mixed-effects models adjusted for demographics and/or traditional CVD risk factors and centre will be used to assess the association between the arms (placebo/rosuvastatin) and each of the following parameters at week 0, 12, 24, 48, 72 and 96. We will test the interaction term between the arms and time (Month 0, 6, 12 and 24) to determine whether the rate of progression of the following parameters differed between arms (rosuvastatin versus placebo): Fasting Total Cholesterol, low-density lipoprotein (LDL)-cholesterol, high-density lipoprotein (HDL)-cholesterol, triglycerides and glucose.

Biomarkers of inflammatory process (sCD14, sCD163, neopterin, S-VCAM-1, adiponectin, CCL2, inflammatory (CD16+) monocyte expression of CD38, CX3CR1 and CD11b) will be

analysed using the same kind of regression with the same adjustments as described above including (LDL)-cholesterol and (HDL)-cholesterol.

The rate of adverse effects (symptomatic and biochemical) from the safety report will be summarized using frequency and percentage.

All efficacy analyses will compare the randomised treatment groups on an intention to treat basis regardless of treatments received during the study, including all patients with data at randomisation and at least one follow-up visit. Primary endpoint analyses will use a last value-carried forward approach for any patients permanently lost to follow-up. Secondary endpoints analyses will only include available data.

Statistical analysis will be performed using STATA Release 12.0 or updated version (Stata Statistical Software: Release 12.0, Stata Corporation, and College Station, USA).

We plan to recruit 102 patients. Drop outs will not be replaced unless the number surpasses the attrition rate of 15%.

An interim analysis will be performed at 48 weeks. The final analysis at 96 weeks will be conducted when all patients will have completed the follow-up visits or have been permanently lost to follow-up, and the study database is signed off as checked and complete.

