## 5 Flow Chart

Assessment	Screen	Baseline	Post randomization				
Week	-4	0	12	24	48	72	96
Written Informed consent	X						
Inclusion / exclusion criteria	X						
Demographic questionnaire a	X						
Physical examination b	X	X			X		X
Compliance assessment c					X		X
Weight & Height measurement d	X				X		X
Adverse event assessment e		X	X	X	X	X	X
Risk Score Calculation f	X						
Laboratory Assessments							
T Cells	X		X	X	X	X	X
HIV RNA viral load	X		X	X	X	X	X
FBE g	X	X	X	X	X	X	X
Biochemistry h	X	X	X	X	X	X	X
Fasting Lipids/glucose i	X	X		X	X		X
hsCRP		X	X				X
Research Blood samples j		X	X		X		X
Structural assessments							
Carotid IMT k	X				X		X
Pulse Wave Velocity l	X				X		X

a Demographic data, medical history and medication questionnaire (will be performed with a trained interpreter if required)

b Includes blood pressure measurement, cardiovascular examination; electrocardiogram (ECG) at screening visit only

c See appendix 17.2: Compliance self-assessment questionnaire and visual analogue scale

d Height will only be measured at screening visit. Body Mass Index (BMI) will be calculated at screening and 12 and 24 month post randomisation

e Unscheduled visits may be performed for safety/tolerability concerns

f Framingham (FRS) and Data Collection on Adverse Events of Anti-HIV Drugs (D.A.D) risk scores calculated

g Full Blood Examination: Haemoglobin, White cell count, Lymphocyte count, Neutrophil count, Platelet count

h Including sodium, potassium, bicarbonate, chloride, calcium, phosphate, urea, creatinine; Liver function tests (LFTs): alanine aminotransferase (ALT), alkaline phosphatase (ALP), total protein, albumin; creatinine phosphokinase (CPK), pregnancy screen in women with child bearing potential

i Participants will fast overnight and have bloods taken in the morning for total cholesterol (TC), low-density lipoprotein cholesterol (LDL), high-density lipoprotein cholesterol (HDL), triglycerides (TG) and glucose

j Blood for markers of innate immunity and inflammation; see Section 11.2 for full description of testing to be performed and stored bloods for future projects

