#### Assessments

1. Demographic data, medical history and medication questionnaire to be completed
2. Full physical examination including:
  - a. Height and weight
  - b. Assessment of peripheral pulses
  - c. Blood pressure
  - d. ECG
3. Laboratory assessments
  - a. FBE and biochemistry
  - b. Beta HCG for all women of child bearing potential
  - c. Fasting metabolic assessment
  - d. HIV viral load and CD4+ T cell count (and percentage)
4. Structural assessments
  - a. cIMT
  - b. cPWV (\*Melbourne Participants only)
5. Calculations
  - a. BMI

- b. Creatinine clearance
- c. FRS
- d. D.A.D. risk score

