#### **12.5 Baseline visit**

Participants will be required to present to the study site having fasted overnight for at least 12 hours (no food, caffeine or caloric drinks; free water is encouraged)

Assessments performed:

1. Targeted physical examination and updated history, assessment for new concomitant medications
2. Adverse event assessment
3. Laboratory assessments
  - a. Biochemistry
  - b. Fasting metabolic assessment
  - c. hsCRP
  - d. Markers of innate immunity and inflammation
  - e. Storage of plasma and PBMCs (\*Melbourne participants only) for possible further analysis in the future

Patients will be provided with a three (3) month supply of the study medication and educated regarding possible clinical signs of potential adverse events (muscle ache, fever, abdominal pain, jaundice, rash); regardless of randomisation. Patients will also be provided with contact details for study co-ordinators in case of adverse event.

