### **12.2 Time windows**

The baseline visit will occur within four (4) weeks of screening to allow for laboratory assessments to be completed and FRS to be calculated confirming eligibility. Study visits at weeks 12 and 24 have a visit window of +/- 14 days (to allow for scheduling of structural assessments and subject convenience). Study visits at weeks 48, 72 and 96 have a visit window of +/- 6 weeks.

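### Fasting lipids and glucose are measured twice before treatment, but the section 17 model names only week 0; using both values would gain precision, by an amount the documents cannot fix

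*Combined protocol and SAP*

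**What the plan says.** The fasting panel (total cholesterol, LDL, HDL, triglycerides, glucose) is marked in the flow chart (section 5) at screening, baseline and weeks 24, 48 and 96. The visit lists agree: section 12.1 has "c. Fasting metabolic assessment" at screening and section 12.5 has "b. Fasting metabolic assessment" at the baseline visit. Both visits require a fast of at least 12 hours. On timing, "The baseline visit will occur within four (4) weeks of screening" (Time windows, end of section 12). Study medication is first supplied at the baseline visit, so both panels precede treatment.

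Section 17, under the secondary endpoints, relates arm to "each of the following parameters at week 0, 12, 24, 48, 72 and 96", using repeated measures mixed models. It then tests the "interaction term between the arms and time (Month 0, 6, 12 and 24") to see whether the rate of progression differs between arms. The models are "adjusted for demographics and/or traditional CVD risk factors and centre". The screening panel is not named as a time point or as a covariate.

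**The concern.** A single pre-treatment value carries its full visit-to-visit noise into every comparison with baseline. A second value from the same person, taken under the same fasting conditions a few weeks earlier, removes part of that noise, and the sample is already scheduled.

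The endpoints concerned are secondary objective 3 and secondary outcome 4 in section 7.2. A large LDL effect would be clear either way. Precision matters more for smaller effects, which may include glucose; section 10.8 lists diabetes among the frequent side effects. There is also a practical gap: the plan has two candidate baselines for these parameters, no rule for combining them, and no rule for a participant whose week 0 fasting sample is missing.

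**Working it through.** **Figures in the plan.** There is none to reproduce for these endpoints: the documents give no SD, correlation or power for lipids or glucose. The only power calculation (section 6.6) is for cIMT. An exact two-sided 1% t-test with 44 per group, a difference of 0.076 mm and an SD of 0.09 mm gives power 0.905, so that figure stands, but it does not bear on this point.

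**Inputs.** Pre-treatment panels: p = 1 (week 0) or p = 2 (screening and week 0). Follow-up panels: r = 3 (weeks 24, 48, 96). Section 17 also lists weeks 12 and 72, but no fasting panel is scheduled then (flow chart, sections 12.6 and 12.9). The within-person correlation ρ is assumed. Variances are in units of the single-visit variance and refer to the estimated arm difference.

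**Equal correlation between all visits.**
- Change from baseline: (1 − ρ)(1/p + 1/r). For r = 3, the ratio of p = 2 to p = 1 is (1/2 + 1/3)/(1 + 1/3) = 0.625, a 37.5% reduction at any ρ. For r = 1 it is 1.5/2 = 0.75, a 25% reduction.
- Baseline-adjusted: [1 + (r − 1)ρ]/r − pρ²/[1 + (p − 1)ρ]. At ρ = 0.5 and r = 3: 0.667 − 0.250 = 0.417 with one value and 0.667 − 0.333 = 0.333 with two; the ratio is 0.80.

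| ρ | Mean of three, change | Mean of three, adjusted | One visit, change | One visit, adjusted |
|---|---|---|---|---|
| 0.5 | 37.5% | 20.0% | 25% | 11.1% |
| 0.6 | 37.5% | 24.1% | 25% | 14.1% |
| 0.7 | 37.5% | 27.9% | 25% | 17.0% |
| 0.8 | 37.5% | 31.4% | 25% | 19.8% |

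- Linear slope: the variance is inversely proportional to the sum of squared deviations of the times. Months 0, 6, 12, 24 give 315. A second value at month 0 gives 403.2, a reduction of 1 − 315/403.2 = 21.9%. Placing it at −0.92 month gives 24.9%.

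**Pre-treatment values closer to each other than to follow-up.** Let a be the correlation between the two pre-treatment values, and b that between pre-treatment and follow-up and among follow-ups.
- Change, mean of three: from 1 + (1 + 2b)/3 − 2b to (1 + a)/2 + (1 + 2b)/3 − 2b.
- Adjusted, mean of three: from (1 + 2b)/3 − b² to (1 + 2b)/3 − 2b²/(1 + a).
- For one visit, replace (1 + 2b)/3 by 1.

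Example, adjusted, one visit, a = 0.9, b = 0.6: 1 − 0.36 = 0.640 falls to 1 − 0.72/1.9 = 0.621, a 3.0% reduction. Over six pairs with a from 0.7 to 0.9 and b from 0.5 to 0.7, the mean of three gains 5-18% (adjusted) or 9-25% (change), and one visit 3-11% or 6-17%. A correlation that decays exponentially with time (starting at 0.7-0.9, decay constant 30 or 60 months) gave 6-25% for the mean of three and 2-14% for week 96 alone.

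**What this does to power (illustration, all assumed).** Take 43 per arm (102 × 0.85 / 2), two-sided 5%, and an effect of 0.5 SD of the single-baseline contrast. Power is Φ(0.5·√(43/2)/√ratio − 1.96): 0.640 with week 0 alone, 0.66 after a 5% cut, 0.736 after 20%, 0.763 after 25% and 0.835 after 37.5%. At 1 SD or more it exceeds 0.99 in every case.

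**The case against.** The strongest reply is that taking baseline at the start of treatment is a standard, defensible choice, so this is a matter of efficiency and not a mistake. That stands.

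A reader might infer that the plan gives up 20-38% of the variance. The documents do not support that as a fact. The range needs equal correlation across visits, a ρ of at least 0.5, and a contrast averaged over the three follow-ups. Section 17 speaks of a rate of progression and section 7.2 of effects after 6, 12 and 24 months, so a slope or a single visit is at least as natural a reading. Panels at most four weeks apart may well resemble each other more than panels 24 to 96 weeks later, and then the gain is smaller.

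A reader might also infer that the screening panel is excluded. The open covariate list could admit a screening lipid or risk score, so exclusion is not stated; but an unspecified list does not commit the plan to using it either. Section 17's time labels are also loose: cIMT is scanned before treatment only at screening, yet that time point is called baseline.

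Finally, screening lipids help decide entry (total cholesterol, triglycerides, the HDL rule and the Framingham score, sections 9.1 and 9.2). The screening values are therefore truncated and subject to regression to the mean. This acts before randomisation and does not bias the arm comparison, but it can lower their correlation with later values and shift their mean from that at week 0.

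**Conclusion.** The point holds as an inexpensive improvement, not as an error. Two comparable pre-treatment fasting panels are collected, the lipid and glucose model starts at week 0, and the screening panel is not named in it. Every correlation pattern computed above shows a gain from using both.

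The size depends on assumptions that the documents cannot settle: about 20-38% (mean of three follow-ups), 22-25% (linear slope) or 11-25% (one visit) if correlation is equal at 0.5-0.8, and about 3-25% if the two pre-treatment values correlate at 0.7-0.9 with each other and 0.5-0.7 with follow-up. Below ρ = 0.5 the adjusted gain is smaller still: at 0.3 it is 10.9% for the mean of three and 5.3% for one visit. Any gain is confined to the five secondary parameters.

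**What to change.** Add a sentence to section 17, before unblinding, choosing one of these for total cholesterol, LDL, HDL, triglycerides and glucose:

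- baseline is the mean of the screening and week 0 fasting values, or the available one if the other is missing; or
- the screening value enters as an additional pre-treatment covariate. Here week 0 should also be a covariate, with only the follow-up values as outcomes. If week 0 stays among the outcomes with a free arm term, a screening covariate with a time-constant coefficient cancels from each person's change and leaves the arm-by-time contrast unimproved.

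Do not model screening and week 0 as two visits sharing one mean, because the eligibility cut-offs can make their means differ.

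The cost is the added text; no new sample is needed. The downside is that within-arm changes from baseline become slightly harder to interpret, since part of the baseline was used for selection. In the same edit, reconcile the listed weeks 12 and 72 with the sampling schedule.

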#### 6.4 Selection of doses

The Jupiter study, using a rosuvastatin dose of 20 mg daily, demonstrated reductions in LDL cholesterol by 50% and hsCRP by 37%; resulting in a 50% reduction in vascular events. The METEOR study reported a significant reduction in cIMT progression after 12 months of rosuvastatin therapy with the divergence continuing to increase with further follow-up out to 24 months. Most rosuvastatin (90%) is excreted unchanged, while 10% undergoes limited metabolism by cytochrome P450 2C9. Pharmacokinetic studies of drug-drug interactions in healthy volunteers have shown that protease inhibitors (PI) in current use caused a 2.4-4.7 fold increase in Cmax and 1.5-3 fold increase in AUC for rosuvastatin. For the participants receiving a non-PI based cART regimen, a dose of 20 mg rosuvastatin (1 x20 mg tablet) will be used. Participants on any PI-based cART regimen will receive 1 X 10 mg rosuvastatin (effective exposure 20 mg daily).

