### 7.2 Secondary Objectives

Secondary objectives are to determine in HIV positive patients:

1. The safety profile of rosuvastatin
2. The effect of rosuvastatin on vessel wall function and biomarkers of atherosclerosis and innate immune activation
3. The effect of rosuvastatin on fasting lipids and glucose
4. Whether baseline measures of immune activation and inflammation predicts cIMT or progression of cIMT
5. Whether a change in measures of immune activation and inflammation from baseline after three months of rosuvastatin therapy predicts progression of cIMT

Secondary outcome measures include:

[figure not shown]
1. The rate of adverse effects (symptomatic and biochemical) between the two treatment arms
2. The effect of rosuvastatin on cIMT and cPWV
3. The effect of rosuvastatin on immunological and inflammatory markers (including sCD14, sCD163, neopterin, S-VCAM-1, adiponectin, CCL2, inflammatory (CD16+) monocyte expression of CD38, CX3CR1 and CD11b)
4. The effect of rosuvastatin on fasting total cholesterol, LDL, HDL, TG and glucose levels after 6, 12 and 24 months of therapy
5. The relationship between baseline measures of sCD14, sCD163, and neopterin and baseline cIMT
6. The relationship between baseline measures of sCD14, sCD163, and neopterin and rate of progression of cIMT
7. The relationship between change from baseline to 3 months in markers of immune activation and inflammation (sCD14, CCL2, and inflammatory (CD16+) monocyte phenotypic expression of CD38, CD11b) and progression of cIMT at 12 and 24 months.

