### **Markers of Innate immunity and inflammation**

Markers of Innate immunity and inflammation will be measured at baseline, and weeks 12, 48, and 96.

For participants recruited in Melbourne only: A panel of innate immune markers selected from HaCH including monocyte markers (CD14, CD16) of activation (CD38), of expression linked to migration, adhesion and progression of atherosclerotic plaque (CD11b, CX3CR1) will be performed.

In participants from both sites in plasma, markers of inflammation (IL6, sCD163) and monocyte activation / chemokine ligands (sCD14, neopterin, CCL2), S-VCAM-1 and adinopectin will be measured.

High sensitivity C-reactive protein (hsCRP) will be performed by the AH laboratory according to standard protocols

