### **12.9 Week 72 visit**

Fasting NOT required for this visit

Assessments performed:

1. Assessment for adverse events
2. Laboratory assessment for:
  - a. Biochemistry
  - b. HIV Viral load and CD4+ T-cell count (and percentage)

Patients will be provided with a six (6) month supply of the study medication

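### Do the biomarker models adjust away part of rosuvastatin's effect by including LDL-C and HDL-C?

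*Combined protocol and SAP*

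**What the plan says.** The secondary-endpoint part of section 17 describes two linked sets of models. Fasting lipids and glucose are compared between arms with repeated-measures mixed models, adjusted for demographic variables and/or conventional cardiovascular risk factors, and for centre. These are said to cover "each of the following parameters at week 0, 12, 24, 48, 72 and 96", while the arm-by-time interaction is tested at months 0, 6, 12 and 24. The biomarkers are then to be "analysed using the same kind of regression with the same adjustments as described above including (LDL)-cholesterol and (HDL)-cholesterol". The section adds that "Secondary endpoints analyses will only include available data" and that efficacy comparisons follow the randomised groups.

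The outcome these models serve is given in section 7.2: "The effect of rosuvastatin on immunological and inflammatory markers". Section 11.2 fixes the sampling times: "Markers of Innate immunity and inflammation will be measured at baseline, and weeks 12, 48, and 96". In the section 5 flow chart the row "Fasting Lipids/glucose" is marked at screening and at weeks 0, 24, 48 and 96, but not at weeks 12 or 72. Section 12.9 says of week 72: "Fasting NOT required for this visit". Section 6.4 cites a trial of rosuvastatin 20 mg in which LDL cholesterol fell by 50%.

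**The concern.** The sentence names two covariates that the study drug is expected to change and gives them no time point. If an analyst entered the LDL-C and HDL-C measured at each visit, the arm coefficient would be conditioned on a consequence of treatment. It would then estimate the effect of rosuvastatin not passing through lipids, whereas section 7.2 asks for the whole effect. A real anti-inflammatory effect could be under-reported and its standard error would rise.

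There would also be a data problem. Biomarkers are drawn at week 12, when section 6.3 expects the change to be visible, but no lipids are scheduled then. With available data only and no carry-over rule, a visit-matched covariate would drop that visit. Two analysts following the same sentence could therefore report different results. Only secondary biomarker endpoints are at stake; the primary cIMT analysis does not use this model.

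**Working it through.** The plan states no power or effect size for any biomarker, so it has no figure of its own to reproduce here. The sample size in section 6.6 concerns cIMT only. The check takes each reading in turn and then asks which one the text supports.

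**On-treatment LDL-C: precision.** Input from the documents: the 50% fall (section 6.4). Assumed, because the documents do not give them: mean LDL-C of 2.5 to 3.5 mmol/L and within-arm SD of 0.6 to 1.0 mmol/L. With 1:1 allocation and d = 0.5 × mean, the share of arm explained by LDL-C is R² = (d²/4) / (d²/4 + SD²). The variance inflation factor is VIF = 1/(1 − R²), and the standard error is multiplied by √VIF. If LDL-C also correlates r with the biomarker within arm, the multiplier is √(VIF × (1 − r²)).

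| Mean, SD | d²/4 | R² | VIF | SE, r = 0 | SE, r = 0.5 |
|---|---|---|---|---|---|
| 2.5, 1.0 | 0.391 | 0.28 | 1.39 | +18% | +2% |
| 3.0, 0.8 | 0.563 | 0.47 | 1.88 | +37% | +19% |
| 3.5, 0.6 | 0.766 | 0.68 | 3.13 | +77% | +53% |

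**On-treatment LDL-C: power and bias.** A simulation took 44 per arm, one post-baseline visit, biomarker SD 1, a true effect of 0.6 SD, a correlation of 0.7 between baseline and on-treatment LDL-C, and a two-sided 5% test. All of these except the 44 are assumptions.

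- No lipid covariate: SE about 0.21, power about 80%.
- Baseline LDL-C: SE about 0.21, power about 79%.
- On-treatment LDL-C: SE 0.25 to 0.38, power 65% to 36%, with no bias because no effect was routed through LDL-C.
- If 30% of the effect ran through LDL-C, the on-treatment model would target 0.7 × 0.6 = 0.42 SD.

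A second simulation set the direct effect at −0.2 SD, the LDL-C shift at −1.0 to −2.0 SD and the biomarker slope on LDL-C at 0 to 0.3. The true total is −0.2 + shift × slope, so it runs from −0.2 to −0.2 − 2.0 × 0.3 = −0.8 SD. The model with arm alone and the model with arm plus baseline LDL-C both recovered the total in every scenario. The model with on-treatment LDL-C returned about −0.2 throughout. At zero slope all three agree.

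**On-treatment lipids: records.** Plasma markers: 102 participants × 4 visits = 408 planned records, of which 102 fall at week 12. Melbourne-only monocyte markers: 72 × 4 = 288, of which 72 fall at week 12.

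**Baseline lipids.** Week-0 values are collected before the first dose is dispensed (sections 5 and 12.5). Treatment has not touched them, they are available for every biomarker visit, and they leave the estimate and its precision as they would be without them.

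**Which reading the text supports.**

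- The covariates being carried over are demographic variables, cardiovascular risk factors and centre. LDL-C and HDL-C belong naturally among the risk factors. They could not adjust the lipid models just described, where they are the outcome; naming them for the biomarkers puts them back.
- Section 17 mentions no time-varying covariate anywhere.
- Visit-matched lipids do not fit the biomarker schedule, because week 12 has none. Week-0 lipids fit all four biomarker visits.
- Section 17 commits the efficacy analyses to a comparison of the randomised arms, which baseline adjustment preserves.

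**The lipid weeks.** Weeks 12 and 72 in the lipid-model sentence have no scheduled lipid sample. The interaction times in the same paragraph, months 0, 6, 12 and 24, match weeks 0, 24, 48 and 96 in the flow chart and the times in section 7.2. With available data only, the models run on those four visits whichever list is followed.

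**The case for a change.** The best case for acting is that the baseline reading is nowhere stated. LDL-C and HDL-C otherwise appear in section 17 only as repeated outcomes. They are named as covariates for the biomarkers but not for cIMT, which might signal an interest in effects beyond lipid lowering; section 6.3 does describe statins as immune modulators. No lipid-free biomarker model is planned as a safeguard, and settling the timing in advance would cost a few words and prevent a choice made after seeing results.

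What stands is that the time point is missing, that nothing else in the documents supplies it, and that on-treatment adjustment would not give the effect named in section 7.2. What does not stand is the step from there to an expected harm. Modelling lipids as outcomes in one paragraph does not make them visit-matched covariates in the next, and the contrast with cIMT is equally explained by lipids already counting among its risk factors. The lower power, the 0.42 SD estimate and the 102 missing records are consequences of a choice the plan does not make. The first two rest on inputs the documents do not give, and they come from different scenarios: the power loss assumes no effect through LDL-C, the reduced estimate assumes there is one.

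**Conclusion.** No change to the plan follows. The sentence leaves a covariate definition unstated in a secondary analysis, and the ordinary choice, week-0 LDL-C and HDL-C, is available, fits the schedule and leaves the treatment comparison intact. On that reading there is no bias, no meaningful loss of precision and no lost visit.

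Only if on-treatment values were used would the arm comparison depart from the total effect. The size of that departure is LDL-C shift × biomarker slope: 0 to 0.6 SD over the assumed range, and zero if the slope is zero. The documents give no slope, so it cannot be estimated for this trial. The conclusion rests on judging that a statistician given this text would use baseline lipids; the text permits the other reading but does not favour it. The primary cIMT analysis, the sample size and the planned relation of week-12 biomarker change to cIMT progression are unaffected. The mismatch in lipid weeks is a clerical slip that alters no result, since no lipid samples are scheduled at weeks 12 and 72.

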#### 10.8 Warnings and precautions

##### **Musculoskeletal reported side effects**

HMG-CoA reductase inhibitors (statins) have been associated with rare cases of severe myopathy and rhabdomyolysis, accompanied by increases in creatine kinase (>10x upper normal limit), myoglobinuria, proteinuria, and renal failure, mainly observed in 40mg daily dosage. Concomitant use with gemfibrozil (fibrin acid derivatives), niacin, cyclosporine, erythromycin (macrolides) or azole antifungals may increase the incidence and severity of musculoskeletal side effects. Milder forms of myotoxicity (i.e., myalgia) are commonly reported and occur in approximately 5% to 7% of patients taking a statin drug.

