### **12.1 Withdrawal visit**

For participants that fulfil any of the withdrawal criteria above a withdrawal visit is performed if the participant agrees. All assessments made during the withdrawal visit can be recorded on the CRF (unscheduled visit). This visit will include, but is not limited to, a targeted medical review and physical examination, laboratory examination for safety reasons (chemistry and haematology), pregnancy test for women and study drug return. Tests performed can vary according to the judgement of the study physician.

Clinical or biological abnormalities perceived at the withdrawal visit will be followed at an interval decided by the study physician, until they are resolved or baseline values obtained.

Participants that withdraw from the study may be contacted by telephone at study end for vital status, unless they refuse and this is documented.

In Australia: In the event of withdrawal of consent by the participant, the Form for withdrawal of participants is completed.

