## **13 Adverse Events**

An AE is defined as follows:

Any untoward medical occurrence in a clinical investigation subject administered a medicinal product and which does not necessarily have a causal relationship with this treatment. An AE can therefore be any unfavourable and unintended sign, symptom, or disease temporally associated with the use of a medicinal product, whether or not considered related to the medicinal product.

Pre-existing or recurrent conditions that occur during the study should not be considered as AEs unless they change in frequency or severity.

All AEs that occur from the time the subject consents to participate in the study and throughout the duration of the study shall be recorded as an AE in the individuals CRF.

At the final study visit (week 96) any ongoing adverse events deemed related to study drug will be followed up for a minimum of 30 days and until resolution.

In case a treatment interruption is needed during the treatment period in the event of a suspected toxicity, the subject will not automatically be withdrawn from the trial, as long as treatment interruption does not exceed 4 weeks.

AEs and SAEs will be categorised and recorded as per the modified Division of AIDS table for grading the Severity of Adverse Events (see Appendix 22.6). Causal relationship of AEs and SAEs to the trial and the study medication will also be assessed.

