### Efficacy data

- cIMT data (primary endpoint measure)

Primary outcome measures (cIMT) and the first secondary outcome measure (adverse effects) will be analysed. Based on these analyses, the DSMB will make recommendations regarding the continuation, modification or termination of the trial.

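### The first secondary outcome compares adverse effect rates between arms, but Section 17 plans only frequencies and percentages, with no arm contrast and no interval

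*Combined protocol and SAP*

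**What the plan says.** Section 7.2 lists as outcome measure 1 "The rate of adverse effects (symptomatic and biochemical) between the two treatment arms". Section 15 treats it as the leading secondary outcome for the 48-week interim review: "Primary outcome measures (cIMT) and the first secondary outcome measure (adverse effects) will be analysed".

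The method is one sentence in Section 17, item 2: "The rate of adverse effects (symptomatic and biochemical) from the safety report will be summarized using frequency and percentage". Two nearby sentences might be expected to fill it out. One reads "All efficacy analyses will compare the randomised treatment groups on an intention to treat basis", which covers efficacy only. The other reads "Secondary endpoints analyses will only include available data", which settles what happens to missing values but gives neither a contrast nor a denominator.

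Section 13 sets the recording window: "All AEs that occur from the time the subject consents to participate in the study". Section 10.8 gives the only adverse effect frequency that helps in judging precision, that milder muscle symptoms "occur in approximately 5% to 7% of patients taking a statin drug".

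**The concern.** The outcome is a comparison, and the analysis is a description. As worded, the analysis sentence does not commit to showing the arms side by side, to estimating how far apart they are, or to stating how precisely that is known. Section 17 does name a between-arm test, with a threshold, for missing IMT measurements, so it specifies more for missing scans than for harms.

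Two things are at stake. First, in a trial of this size a few events per arm can look like reassurance when the data exclude very little, and an interval is the simplest guard against that reading. Second, one of the stopping rules in Section 15 turns on whether serious adverse effects are significantly more frequent in one arm. That is a between-arm judgement, and no estimator or interval is given for it.

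**Working it through.** **Inputs.** Section 6.6 gives a total of 102 participants, and allocation is 1:1, so there are 102/2 = 51 per arm. The plan states no precision or power figure for adverse effects, so there is nothing of that kind to reproduce. The 102 itself follows from 44 per arm: 88 × 1.15 = 101.2, raised to 102. The myalgia frequency of 5% to 7% on a statin is from Section 10.8; 51 × 0.05 = 2.6 and 51 × 0.07 = 3.6, or about 3 to 4 cases on rosuvastatin. The event counts below are illustrations.

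**Interval for a difference (Newcombe).** For each arm take the Wilson limits (l, u), with p = x/n and z = 1.96:

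(p + z²/2n ± z√[p(1−p)/n + z²/4n²]) / (1 + z²/n)

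The limits for D = p1 − p2 are then D − √[(p1−l1)² + (u2−p2)²] and D + √[(u1−p1)² + (p2−l2)²].

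- 3/51 v 3/51: each arm is 5.88% (Wilson 2.02% to 15.92%). D = 0, and the half-width is √(3.86² + 10.04²) = 10.8 points.
- 4/51 v 1/51: 7.84% (3.09% to 18.50%) and 1.96% (0.35% to 10.30%). D = 5.9 points. Lower limit 5.88 − √(4.75² + 8.34²) = −3.7; upper limit 5.88 + √(10.66² + 1.61²) = 16.7.
- 0/51 in one arm: the exact two-sided 95% upper limit is 1 − 0.025^(1/51) = 7.0%.

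**Precision in general.** The simple half-width 1.96√[2p(1−p)/51] is 8.5 points at a 5% rate in both arms, 9.9 at 7%, 11.6 at 10% and 17.8 at 30% (the last two rates are assumed). For a formal comparison at two-sided 5% and 80% power, the smallest detectable contrast is about 5% v 24.5%. That is why estimation is the realistic aim.

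**Does unequal follow-up distort the percentages?** The documents give 15% total dropout and nothing by arm, so this is a sensitivity check on assumptions. Let the event hazard λ be the same in both arms. Let withdrawal be independent of events, with hazard μ = −ln(1−w)/T, where T = 96/52 = 1.846 years, and assume no recording after withdrawal. The chance that an event is seen is λ/(λ+μ) × (1 − exp[−(λ+μ)T]). Take w = 5% on placebo and 15% to 25% on rosuvastatin (μ = 0.028 v 0.088 to 0.156 per year).

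| True event frequency, both arms | Placebo, w = 5% | Rosuvastatin, w = 15% | Rosuvastatin, w = 25% | Apparent gap (points) |
|---|---|---|---|---|
| 5% over 96 weeks (λ = 0.028) | 4.9% | 4.6% | 4.4% | 0.3 to 0.5 |
| 7% over 96 weeks (λ = 0.039) | 6.8% | 6.5% | 6.1% | 0.4 to 0.7 |
| λ = 0.5 per year (assumed) | 59.0% | 56.3% | 53.5% | 2.7 to 5.5 |

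At the protocol's own myalgia frequency the gap is 0.3 to 0.7 points, less than half a participant in 51 (0.007 × 51 = 0.4). With equal withdrawal in the two arms it is zero.

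**The case against.** Descriptive safety tables are common in a trial sized only for cIMT. Because Section 7.2 defines the outcome between arms, the percentages would probably be shown by arm, and a reader could then subtract them and work out an interval. The documents also plan no claim of equal safety. Most of this stands, and it keeps the point modest. It does not remove the point: Section 17 does not actually promise per-arm figures, and person-time cannot be recovered from percentages. It is also fair that several event categories, each with an interval, should not be read as a set of tests; the fix says so.

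A reader might infer something stronger: that withdrawal for toxicity under Section 9.4 shortens follow-up on rosuvastatin and makes it look safer by several points. The documents do not support that. A participant withdrawn for a related SAE or for a CK or transaminase rise already counts as having had an event, so leaving afterwards cannot remove that person from the percentage with at least one event. Later events of other types could be missed. The gap of roughly 3 to 6 points in the last row of the table needs both a high assumed event rate and excess withdrawal unrelated to events.

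Nor is it right that only survival is pursued after withdrawal. Former participants "may be contacted by telephone at study end for vital status", but the same section offers a withdrawal visit with medical review and safety bloods, if the participant agrees, and follows abnormalities found there. Section 14.1 extends SAE reporting to 30 days after the last dose or the end of participation, whichever is longer.

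Events recorded between consent and baseline, a gap of up to four weeks, are balanced in expectation by randomisation. They dilute the comparison slightly but do not bias it.

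**Conclusion.** The point holds as a gap in specification that is cheap to close. A stated comparative outcome has no comparative estimate and no statement of precision. The size of the problem is the width of what would go unreported: about ±8.5 to ±10 points at event rates of 5% to 7% with 51 per arm (simple half-width), and ±10.8 points by Newcombe for equal counts of three. These figures rest on 51 evaluable participants per arm and on illustrative counts; with fewer evaluable, the intervals widen.

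Neither the primary result nor the sample size is affected. Bias from unequal follow-up should not be put forward as a finding: it depends on assumptions, is small for rare events and disappears if dropout is balanced. Follow-up may still differ by arm, which is enough reason for a supportive summary by person-time.

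**What to change.** In Section 17, item 2, replace the adverse effect sentence with wording to this effect:

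*For any AE, any SAE, any grade 3/4 AE or laboratory toxicity, myopathic symptoms, and CK or ALT elevation, the number and percentage of participants with at least one event will be reported by arm with the denominator stated, together with the risk difference (rosuvastatin minus placebo) and its 95% confidence interval (Newcombe or score). These are estimates, not powered tests. Events per 100 person-years will be given by arm as a supportive summary. Events with onset before study medication was dispensed, taken as the baseline visit date, will be listed separately.*

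The baseline visit date is proposed as the cut-off because the baseline CRF in the appendix records the visit date and whether supply was given, but shows no field for the date of the first dose. The scheduled-visit forms give visit dates for person-time, and the adverse event and SAE forms carry onset dates. Using the same table for the interim review would also give the DSMB a defined between-arm estimate.

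The cost is SAP wording and a few more table columns; visits, sample size and clinical rules do not change. The downside is that the intervals will be visibly wide. The change is best made before the unblinded 48-week review.
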